 - Physical Activity (discussing physical activity guidelines and how to support kids to be active on a daily basis)
 - Screen time (discussing screen time guidelines, smart screen time use and strategies to help limit children’s screen time)
 - Family Exercise Activity (a session in which adults and children will be guided through a fun physical activity, such as Zumba).
 - Family Cooking Activity (a session in which adults and children will be guided through preparing a healthy meal.)
 - A sample Family DPP schedule included in this IRB application under “Supplementary Material.”

- 3) **Note on children as participants in the FDPP:** Both the FDPP and National DPP interventions are intended to be delivered primarily to the adult participant (caregiver of the child). For the FDPP, children may be present during child-focused modules as noted above. During these sessions, the children will engage in age-appropriate activities, games and discussions to learn basic concepts about healthy lifestyle behaviors. This would be done separate from the adult caregivers (a separate room or Zoom room, if possible), and then they will join the adult caregivers at the end of the session for a group discussion.
- 4) Concurrent Control Group: The adults in the concurrent control group will be recruited (as detailed below) from participants in the Brancati Center's Diabetes Prevention Program.

Recruitment, Screening Eligibility and Enrollment: Intervention Arm

Recruitment for Intervention Arm:

We will recruit adult participants, and one index child, through several means as detailed in "Section 13". This will include

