1) Recruitment from adults who are outreached for the Brancati Center's Diabetes Prevention Program. After these adults are deemed eligible for the Diabetes Prevention Program for screening, they would be asked the following question by Brancati Center DPP team members "There is a research study for DPP participants that you may be eligible for. This study involves adults in the DPP and children ages 5 through 12 years that they care for. As part of the study, you would be enrolled in a "family-oriented" version of the DPP, which would include some sessions related to children's healthy behaviors in the second half of the program. In addition to you participating in the DPP, you and one child would be asked to complete surveys and provide some other data 3 times during the program, and potentially participate in an interview after the program. You would be compensated \$50 for each of the data collection points. Would you be interested in learning more about the study?" If potential participants are interested, their contact information would then be provided to the Family DPP study team for recruitment and screening eligibility.

2) Flyers in clinical sites and community partner sites, with the flyer also posted to the Brancati Center's Facebook Page and website. We will also request community partner organizations in Baltimore to disseminate the flyers to their community members (such as through in-person events, via e-mail or with announcements, or by posting on their social media sites). We will also advertise via paid Facebook advertisements. We will also request community partner organizations in Baltimore to share with their community members including at in-person events and via e-mail or by posting on their social media sites. We will also advertise via paid Facebook advertisements. The flyers will have a contact study email and also phone number for participants to call. The phone number will be that of a study team member; the email will only be accessible to study team members. A telephone screening script will be used when a study team member discusses the study with potentially interested participants, to assess eligibility. If a participant provides their email address as contact information, we will outreach via telephone and also if needed via email from the [contact] email account.

The email outreach will read:

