 - o **Process Measures: Measures of program feasibility** (other than caregiver attendance, which will be collected as per the DPP protocol as above), including recruitment rate, child attendance, child outcome measurement completion, survey administration time and cost (per group) will be tracked during the study by study team members. **Measures of acceptability** will be collected via a survey tool administered to the adult participants after each child-focused session and at the end of the program (the surveys maybe administered either via telephone, in-person or participants may be asked to complete the survey via a secure RedCAP link). **Measures of fidelity** in Family DPP delivery will be collected via a Fidelity Checklist tool that will be completed by a study team member who will observe the child-focused sessions (being delivered to the adult participants). In addition, coaches will be asked to complete a Coach Reflection sheet at the end of each child-focused or child-related session, which will make note of any timing-related issues with content delivery and content-specific issues (graphics that were unclear, discussion points that should be included in future iterations of the material, etc.)
 - o **Adult-related outcomes:** For adult participants, we will conduct surveys at baseline, around 6 months (after completion of core period of DPP or Family DPP curriculum) and at the end of the program (12 months). These surveys will cover domains including: household demographics, child demographic information, household social determinants of health, adult health behaviors, self-efficacy for behavior change, and parenting self-efficacy. These surveys will be administered either in-person, via telephone or via RedCAP link.
 - o **Child-related outcomes:** For child health behavior outcomes, the adult participant will be asked questions regarding child health behaviors (physical activity, screen time, fruit and vegetable intake, sugary beverage intake, sleep duration). For children ages 9 through 12 years, we will also ask these questions directly of the child; the child will be interviewed with their caregiver present, either in-person or via telephone. For child health outcomes, **specifically change in BMI z-score**, we will collect child height and weight in-person. This will be done in a private space at the community-partner site or the JHM campus (offices of the Brancati Center) or at a location of the participant's preference or choosing.

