 - o **As per our Data Safety Monitoring Protocol** outlined in Section 32 of the IRB application, we will query participants about possible adverse events using the Adverse Events form at 6 and 12 month data collection points.

Data Collection for Concurrent Control Group (Control Arm)

- 1) Data collection associated with Routine Care (DPP protocol):
 - o **Adult-related outcomes:** Adult participants who are part of the Brancati Center's Diabetes Prevention will have data collected relevant to their participation in the program, as per the routine care protocol. This includes data collected as part of the DPP eligibility screening process and program enrollment process. During the program, this includes participants' attendance, weight (either measured if in-person visits, or self-reported) and self-reported physical activity minutes.
- 2) Additional data collection for concurrent control group: For adults in the concurrent control group, we will conduct a baseline survey. This survey will cover domains including: household demographics, child demographic information and household social

determinants of health. The survey may be conducted over telephone or via secure REDCap online link (self-administered).

3) Also, as per our **Data Safety Monitor Protocol** outline in Section 32 of the IRB application, we will query participants about possible adverse events using the Adverse Events form at 6 and 12 month time points via telephone.

b. If your study involves data/biospecimens from participants enrolled under other research studies with a written consent or under a waiver of consent, please list the IRB application numbers for those studies. Please note: Certificate of Confidentiality (CoC) protections applied to the data in source studies funded by NIH or CDC will extend to this new study if the funding was active in 2016. If this situation applies, Section 36, question 6 in the application will need to be answered “Yes” and “Hopkins Faculty” should be selected in question 7. No other documents are required.

For both the adult intervention arm participants and concurrent control group (control arm) participants, we will obtain adult participant attendance data, as well as weight and physical activity data, from the Brancati Center’s Diabetes Prevention Program participant database; these activities are undertaken under IRB protocol “IRB00179397: Evaluation of the Johns Hopkins Diabetes Prevention Program.”

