Not applicable.

7. Plan for reporting unanticipated problems or study deviations.

The plan below is specifically for the **Intervention Arm**.

The PI ([name]) and co-I ([name]) will bear the responsibility for data and safety monitoring. An independent data safety monitor ([name], Assistant Professor, General Internal Medicine) will be employed as well as below.

During data collection points at 6 and 12 months, adult participants would be queried about possible adverse events (AEs), specifically interim ED visits or hospitalizations, for both themselves and the child enrolled in the study. (see uploaded Adverse Events form). Any and all adverse events would be reviewed by the PI, [name] as co-I and also the independent safety monitor for review; adverse events will be reported to the Johns Hopkins School of Medicine IRB, as well as NIH project office according to the prevailing policies of these review bodies. Study team members will receive training regarding adverse event documentation and reporting.

In addition, adult weight changes and child BMI changes will also be reviewed as follows: at 6 and 12 months, a research team member will send to the independent study monitor a report with participant study ID, age and % weight change for adults or change in BMI for children over the past 6 months. Significant changes in adult weight or child weight-for-height over the review period will prompt the independent safety monitor to notify [name] or [name] to refer the participants to their primary care physician for additional evaluation.

Of note, the Brancati Center DPP clinical program has team members who provide medical oversight of all participants in the DPP, and adult participants in the study will also be under this as per routine care. During weekly team meetings as part of routine care, adult participants weight changes are reviewed for all participants.

8. Payment and Remuneration

Intervention Arm

Specific to study procedures, the adult participant (as the representative of the adult-child dyad) will be remunerated via \$50 gift cards with completion of data collection at each time point (baseline, 6 month, 12 month), for a maximum of \$150 related to study procedures. In addition, the Brancati Center's DPP provides program-related supports that will continue to be the same for all participants.

Concurrent Control Group (Control Arm)

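### As written, adverse events are solicited only at months 6 and 12 and only as ED visits or hospitalizations, so lesser harm to a child during the child-focused sessions between those points is not explicitly sought

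*Combined protocol and SAP*

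**What the plan says.** Section 7, which applies to the intervention arm, describes the solicitation: at months 6 and 12 adults are "queried about possible adverse events (AEs), specifically interim ED visits or hospitalizations", with the question covering both the adult and the enrolled child. It then sets a much wider scope for review: "Any and all adverse events would be reviewed by the PI", with the co-investigator and an independent safety monitor also reviewing. Section 3.a (Data Collection for Intervention Arm) gives the same schedule without the restriction to ED visits or hospitalizations: "we will query participants about possible adverse events using the Adverse Events form at 6 and 12 month data collection points". It refers to a monitoring protocol in Section 32 of the IRB application.

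Section 3.a (Intervention Content Description) puts the child-focused sessions in the post-core period. One of them is the "Family Exercise Activity (a session in which adults and children will be guided through a fun physical activity, such as Zumba"; another has adults and children prepare a meal together. At these sessions, "coaches will be asked to complete a Coach Reflection sheet at the end of each child-focused or child-related session". The sheet is described as noting timing and content issues.

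**The concern.** The promise to review all adverse events can be no wider than what is collected. A sprain during the exercise session, or a food reaction managed at home, at urgent care or by the pediatrician, would not meet the wording of the query. Child participation is what FDPP adds to an established adult program, and children may be as young as 5. The enrollment form records the child's food and other allergies, so the study foresees this kind of risk, but no visible form is described as recording its occurrence.

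The stake is how the pilot's result will be read. Section 3.f says the comparison is meant to inform a larger trial. A report of no child adverse events could reflect the narrowness of the question rather than the safety of the sessions.

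**Working it through.** No power or error-rate calculation applies, and the plan states no figure to reproduce. The check sets the query schedule against the session schedule, then asks what else runs in the gap.

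1. **Query timing.** Sections 3.a and 7 both give months 6 and 12. Section 3.a places these data points "around 6 months (after completion of core period of DPP or Family DPP curriculum) and at the end of the program (12 months".
2. **Session timing.** Section 3.a gives the core period as the first 6 months and the post-core period as a further 6. Child-focused sessions are post-core. The recruitment text agrees, placing the sessions on children's "healthy behaviors in the second half of the program".
3. **Count.** The listed topics are MyPlate, fruit and vegetables, sleep, sugary beverages, physical activity, screen time, family exercise and family cooking: 8 in all, of which 2 are hands-on. Topics scheduled before the month-6 query: 0 of 8. Topics scheduled after it and by month 12: 8 of 8.
4. **Recall.** An event just after the month-6 query is next asked about at month 12, so the longest recall is about 12 − 6 = 6 months. The informant need care for the child only 3 days a week to be eligible (Section 4).
5. **Definition.** Section 7 limits the query to ED visits or hospitalizations. Child events of that kind are covered at month 12. Lesser child events are outside the wording at both time points.
6. **Other collections between months 6 and 12:**
   - Weekly weight review and routine medical oversight (Section 7) continue, but are described for adults only.
   - Child BMI change goes to the independent monitor at months 6 and 12 (Section 7). It would not show a sprain or an allergic reaction.
   - The Coach Reflection sheet (Section 3.a) is described in terms of timing and content.
   - The observer's checklist (Sections 3.a and 6.a) measures fidelity in the sessions delivered to adults.
   - The caregiver survey after each child-focused session (Section 3.a) measures acceptability.

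None of these is described as asking about injury or reaction. FDPP's adult-directed additions, including two supplementary sessions, begin in the core period, and the month-6 query does cover those.

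**The case against.** The strongest objection is that the two queries need not be the whole adverse-event system. Section 7 says study staff will be trained in documenting and reporting adverse events, and a study team member observes the child-focused sessions given to adults. Spontaneous reporting is not spelled out, but neither is it ruled out. The Adverse Events form, Section 32 and the Coach Reflection sheet are not available, and the list of what the sheet covers is open-ended. This stands: the finding concerns what the visible text solicits, not everything that staff might report.

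A reader might go further and infer that no planned collection picks up harm while the child-focused sessions are running, or that lesser events are captured 0% of the time. The documents do not support either. Adult weight review and medical oversight continue through that period, child BMI reaches the monitor, and the unseen forms prevent any claim of zero capture. A reader might also infer that serious child events are missed. They are not: the month-12 query covers interim ED visits and admissions for the child, though late.

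Other points reduce the weight of the concern. Six of the eight topics are mainly discussion. The exercise and cooking sessions are described as guiding adults and children together, so the caregiver takes part. Delivery is expected to be mainly by Zoom. Safety is not among the listed outcomes and there is no stopping rule, so no planned analysis depends on minor events. These points justify a modest rating. They do not close the gap between reviewing all events and asking about two kinds.

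**Conclusion.** The concern holds in limited form. In the visible text, all 8 child-focused topics depend on a single solicited adverse-event query, at month 12, with recall of up to about 6 months. Child harm short of an ED visit or admission, and not visible in BMI, is not explicitly solicited at any time, although Section 7 commits to reviewing every event.

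This rests on three assumptions: that Section 7's restriction describes the actual content of the form, that sessions follow the stated core and post-core timing (the month-6 point is approximate and the sample schedule is not shown), and that Section 32 adds no wider solicitation. If the form or Section 32 is broader, the remaining defect is that Section 7 does not say so. No event rate is given, so the number of events affected cannot be estimated. For a low-intensity behavioral pilot this is a change that should be made because it is cheap; it does not undermine the feasibility objective.

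**What to change.** - Add one incident item to the existing Coach Reflection sheet: injury, food or allergic reaction, or other; adult or child. Have whoever leads the separate children's session complete the same item. In Zoom sessions the leader will need to ask, since an incident may not be visible on screen.
- Send any positive entry to the investigators and the independent monitor when it occurs.
- Reword the month-6 and month-12 query to include any injury or reaction related to program activity, whether or not it led to an ED visit or admission. Section 3.a plans the same form for the control group by telephone, so use the same wording there.
- Report incidents from session forms separately from query responses. The control group has no such form, and pooling the two sources would make FDPP look less safe simply because it was watched more closely.
- If the Adverse Events form or Section 32 already covers lesser events, amend Section 7 to say so.

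The cost is one line on an existing form, a wording change, a minor IRB amendment and review of a few more minor events. No new visit or staff is needed.

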The DPP (and FDPP) interventions are designed for prevention of type 2 diabetes in adults with prediabetes. Some adult participants may progress to type 2 diabetes while participating in the FDPP; the CDC's guidelines are that these individuals can remain in the DPP lifestyle intervention (given the benefits of lifestyle modification). The Brancati Center team confers with the participant's primary care provider if this were to occur (development of type 2 diabetes) to confirm that the participant is recommended to continue in the DPP.

h. Description of what happens to participants receiving therapy when study ends or if a participant's participation in the study ends prematurely.

Participants will be instructed to continue with routine medical care when the program ends or if their participation ends prematurely.

i. If biological materials are involved, please describe all the experimental procedures and analyses in which they will be used.

Not applicable.

4. Inclusion/Exclusion Criteria

Intervention Arm

The study will enroll adult-child dyads in the Intervention Arm.

Adult inclusion criteria will include meeting all of the following:

- 1) CDC national criteria for enrollment in the DPP (as used by the Johns Hopkins Brancati Center's DPP programs):
 - Be 18 years of age or older and not pregnant at time of enrollment
 - Have a body mass index (BMI) of $\geq 25 \text{ kg/m}^2$ ($\geq 23 \text{ kg/m}^2$, if Asian American).
 - Meet either one of the criteria
 1. Have a recent (within the past year) blood test meeting one of these specifications:
 - i. Fasting glucose of 100 to 125 mg/dl (CMS eligibility requirement for Medicare DPP suppliers is 110 to 125 mg/dl)
 - ii. Plasma glucose measured 2 hours after a 75 gm glucose load of 140 to 199 mg/dl
 - iii. A1c of 5.7 to 6.4%.
 2. Clinically diagnosed gestational diabetes mellitus (GDM) during a previous pregnancy
 3. A positive screening for prediabetes based on the CDC or American Diabetes Association Diabetes Screening Test (a brief questionnaire)
- 2) being a primary caregiver of at least one eligible child aged 5 through 12 years at time of recruitment (defined as caring for the child, with a responsibility for the child's food, sleep and activity habits, at least 3 days out of the week)

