Exclusion criteria for adults will reflect CDC national DPP exclusion criteria. Specifically, adults will be excluded if they are: 1) pregnant; 2) have end-stage renal disease; 3) have type 1 or type 2 diabetes. They will also be excluded if they are concurrently enrolled in a structured weight management program.

Children for whom the eligible adult is a primary caregiver (parent or guardian who cares for the child 3 or more days out of the week), will be considered eligible participants if 1) they are aged 5 through 12 years at time of recruitment; 2) they do not have a medical condition which leads to inability to comply with general pediatric dietary or physical activity goals; and 3) they are not concurrently enrolled in a structured weight management program.

Concurrent Control Group

Inclusion criteria for adults in the control group will include meeting all of the following:

- 1) Participant in the Brancati Center's Diabetes Prevention Program, in a group that has started within 6 months of Intervention Arm group start
- 2) Lives with a child less than 18 years of age in their household

5. Drugs/ Substances/ Devices – Not applicable

6. Study Statistics

a. Primary outcome variable.

Primary outcomes will examine process measures.

These will include:

- I. Feasibility measures (measuring recruitment, retention and measurement of outcomes, cost):
 - a. Recruitment rate, measured as % of eligible caregivers consented to study/time
 - b. Caregiver attendance, defined as % of adult, child-focused and all sessions attended
 - c. Child attendance, defined as % of sessions requiring child participation attended
 - d. Survey administration, defined as mean time for administration of surveys
 - e. Total cost per group of program delivery
- II. Acceptability measures
 - a. Including mean scores on Likert scale-based questions re: satisfaction with program content & structure, willingness to recommend to others
- III. Fidelity, as measured by a fidelity checklist that will be completed by a study team member observing the child-focused sessions (specifically, the child-focused sessions delivered to adult participants), and will include measures:
 - a. % of tasks/content delivery per session from coach checklist
 - b. Total & average scores per domain from observer checklist

b. Secondary outcome variables.

Secondary outcome variables will preliminarily examine:

1. Proximal intervention targets

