 - a. Caregiver (adult participant) knowledge and attitudes towards healthy-related behaviors
 - b. Perceived self-efficacy for behavioral change
 - c. Parenting self-efficacy for behavioral change
 - d. Family Home Environment
2. Caregiver (adult participant) Health behaviors and health outcomes
 - a. Physical activity- total minutes of moderate/vigorous physical activity in weeks preceding and whether caregiver meets DPP physical activity goal of 150 minutes/week of moderate-vigorous physical activity; and dietary
 - b. Dietary patterns

- c. Percent weight loss from baseline
- 3. Child health behavior and health outcomes
 - a. Physical activity- minutes/day
 - b. Screen time (hours/day)
 - c. Fruit and vegetable intake
 - d. Sugary beverage intake
 - e. Sleep duration and sleep behaviors
 - f. BMI z-score change
- c. Statistical plan including sample size justification and interim data analysis.

As the main objective of this study is evaluating FDPP feasibility and acceptability measures, sample size is primarily informed by budgetary constraints and our experience recruiting individuals for the DPP as well as recruitment for the study thus far.

Feasibility, acceptability and fidelity measures will be analyzed with descriptive statistics (Table 2). Intervention targets will be analyzed as continuous variables (means or numerical scores). Caregiver and child health behaviors will be analyzed as continuous variables (average value/day) and a binary variable (achievement of goal). The caregiver health outcome will be modeled as a continuous variable (percent of weight loss from baseline) and binary variable (achievement of 5% weight loss goal). The child health outcome is the BMI Z-score, a continuous variable. Within-groups, we will use 1) paired-t tests to analyze pre-post changes (from baseline to 6 months and baseline to 12 months) of continuous variables; and 2) McNemar's exact test to examine pre-post changes in proportion achieving behavioral and outcome goals (binary variables). Between groups, we will use 1) 2-sample t-tests to compare the magnitude of mean group change in values of continuous variables; and 2) Fisher's exact test to compare proportion achieving goals at 6 and 12 months. If continuous variables do not meet distribution assumptions necessary for use of parametric tests (t-tests), we will use appropriate non-parametric tests (Mann-Whitney test or, for paired data, Wilcoxon signed-rank test).

- d. Early stopping rules.

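### The monitor's child report lists change in BMI without sex, BMI level or z-score; adding them costs nothing and lets the same change be read differently in a thin child and a child with obesity

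*Combined protocol and SAP*

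**What the plan says.** Section 7 (Plan for reporting unanticipated problems or study deviations), which applies to the intervention arm, describes a growth and weight review at 6 and 12 months. The independent monitor receives "a report with participant study ID, age and % weight change for adults or change in BMI for children over the past 6 months". The trigger for referral follows: "Significant changes in adult weight or child weight-for-height over the review period will prompt the independent safety monitor" to ask the investigators to send the participant to primary care. No numerical threshold is given.

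Elsewhere the plan uses another measure for children. Section 3.a (Data Collection for Intervention Arm) names the child health outcome as "specifically change in BMI z-score" and says "we will collect child height and weight in-person". Section 6.b lists "BMI z-score change" among the secondary outcomes, and section 6.c treats the BMI z-score as the child health outcome.

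On eligibility, section 4 requires intervention-arm adults to have a BMI of at least 25 kg/m² (23 if Asian American). Children qualify on age (5 through 12 years), on not being in a structured weight management program, and on the condition that "they do not have a medical condition which leads to inability to comply with general pediatric dietary or physical activity goals". Section 3.a also places the Data Safety Monitoring Protocol elsewhere, as "outlined in Section 32 of the IRB application".

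**The concern.** What a given BMI change means in a growing child depends on the child's age, sex and starting point. A fall may be welcome in a child with obesity and a warning sign in a thin one. The listed report gives the monitor age and a difference, but neither the starting point nor a change standardised for age and sex.

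Starting level matters more for the children than for the adults. Every intervention-arm adult enters above a BMI floor and is reported as a percentage of starting weight. The children enter at any BMI, and their change, read as written, is not scaled to anything.

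At stake is whether the monitor, working from the report, can tell which children need referral. This is also the only review of child growth that the plan describes. The weekly weight review in section 7 is described for adults, and the adverse event query covers ED visits and hospitalizations, which would not pick up gradual drift.

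**Working it through.** The plan states no sample size, safety threshold or growth reference, so there is no figure to reproduce. The check compares what the report lists with what a standardised change needs.

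**1. Fields listed for a child (section 7).** Study ID, age, change in BMI: 3 items.

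**2. Inputs to a standardised change.** Writing z(BMI, age, sex) for the z-score, the change is

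Δz = z(BMI_current, age_current, sex) − z(BMI_start, age_start, sex).

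With age known and the interval fixed at about 6 months, this needs age, sex, starting BMI and current BMI: 4 inputs. The report supplies age and d = BMI_current − BMI_start. One BMI level would give the other through d. Still missing are sex and one BMI level: **2 inputs**.

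**3. Generous reading.** If change in BMI is shorthand for change in BMI z-score, the standardised change is already there. The starting level is not: **1 item** missing.

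**4. Can eligibility supply the starting level?** For adults it does in part, through the floor of 25 (or 23) kg/m². For children, section 4 has three criteria: age, no limiting medical condition, no concurrent structured weight management program. Those that set a BMI range: **0 of 3**.

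**5. Illustration.** Starting BMIs of 15, 20 and 30 kg/m² are assumptions, not values from the plan. A change of 1 kg/m² as a share of each is:

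| Assumed starting BMI | Share |
|---|---|
| 15 | 1/15 = 6.7% |
| 20 | 1/20 = 5.0% |
| 30 | 1/30 = 3.3% |

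The first is twice the last, yet a plain difference shows all three children with the same entry. No z-scores are computed because the plan names no growth reference.

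**6. Look-back.** Each report covers the past 6 months. The 12-month report therefore shows change from month 6, not from baseline. A steady change of d per half-year appears as d twice, although the year's change is 2d. The monitor could add the two reports; a baseline column would make that unnecessary.

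**7. Terms for child growth.** Change in BMI and weight-for-height (both section 7) and BMI z-score (sections 3.a, 6.b, 6.c): 3 terms, two of them within the same safety paragraph.

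**8. Availability of the missing items.** Height and weight are measured in person, section 3.c has visits at baseline, 6 and 12 months, and z-score change is a planned outcome. Sex is not named among the collected items, but section 3.a surveys child demographic information, and the planned z-score cannot be computed without it.

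**The case against.** The strongest reply is that section 7 may only summarise a fuller procedure. The monitoring protocol is in Section 32 of the IRB application, so what is shown is that one paragraph omits the fields, not that the monitor will lack them. This stands as a limit on the claim.

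Second, BMI is itself an index of weight for height, and the paragraph opens by speaking of child BMI changes. The wording is loose rather than contradictory. This also stands; the change of term is the minor part of the point.

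Third, the monitor may ask for more, and the investigators hold the data. That is true, but an entry that looks unremarkable gives no reason to ask.

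Fourth, the risk is modest. The children receive guideline-based education and activities, no child weight-loss target is stated, and ED visits and hospitalizations are queried separately. This stands and is why the consequence is rated low.

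Fifth, the undefined word significant is a larger gap than the missing columns, and the fix does not close it. This is correct. However, when referral rests on clinical judgement, the case for giving the monitor the facts needed to judge becomes stronger.

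**Conclusion.** The point holds, as a low-consequence improvement that should be made. As listed, the child report omits two inputs to a standardised change, or one item on the generous reading, in each of 2 reports per child. With no BMI criterion for children, the listed fields cannot separate a fall that is welcome from one that is worrying. No outcome, test or sample size is affected, and the only action that depends on the report is referral to primary care.

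The conclusion rests on section 7 describing the report as it will be sent. If Section 32 already specifies the missing fields, what remains is a wording mismatch. No number of children affected and no z-score size is claimed, because the plan gives neither a sample size nor reference values.

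**What to change.** In section 7, list for each child: study ID, age, sex, baseline BMI, current BMI, and change in BMI z-score over the past 6 months. Reword the trigger so that it refers to significant changes in adult weight, or in child BMI or BMI z-score, over the review period. The threshold can stay with the monitor's clinical judgement. If Section 32 of the IRB application already says this, bring section 7 into line with it.

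The cost is a few columns in an existing report and one changed term. No new body measurement, visit or analysis is needed.
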